9.1. Flow chart

A detailed flow chart with number of invited, reasons for exclusions and reasons for dropouts will be reported for the participating GPs in a Figure.

9.2. Handling of missing data

Throughout the study period (21 months) participating GPs will be absent from the clinic due to vacation, short illness, course participation etc. This absence will result in variation in the GPs' activity (remunerations codes and referrals). For this study, we will assume that the participants' planned absence from the clinic is comparable. Still, extraordinary absence from the clinic due to e.g. long-term illness or longer vacation will result in missing data. Missing data for participants will also occur if a participant withdraws from the study or we are unable to extract data through the medical record system from a participant in a given month. Finally, missing data will occur if the clinic does not provide individual GP data to PLSP.

We will impute for missingness in two steps.

1) If individual data on a GP is missing, we will carry over data from the practice level. This can be done if the GP has no other colleagues participating in the study and if it will be reasonable to assume an overlap between the GPs data and practice level data.

2) In other cases of missingness, we impute data based on available data separately for each of the ten clusters based on available data from the cluster and the clinic.

10. Assignment of clusters

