6. Link to the individual assignments to be completed by participants during the learning process. The teachers on the course have the opportunity to comment and respond in the assignment.
7. A link to an online logbook where the individual participant can note conducted POCUS examination during the learning process (date, type of POCUS, focus during the examination, reflections afterwards). A template specifies the number of examinations recommended at each phase in the educational intervention.
8. A direct chat opportunity with the teachers, where participants can have access to guidance and support from the course teachers. It is also possible to upload scanning images or videos for review by the teachers.
9. The individual structured feedback for all scanning modalities collected at teaching seminar 2 and 3.
10. Access to Pre/post self-quizzes before and after each training seminar and access to the results.

Participants will receive a notification by email or on their phones, when there is activity on the online platform. The overall purpose of this online platform is to support the participant in the continuous learning process. We aim to create awareness about the learning process, individual focus points and goals, the importance of training and gaining experience, and to make guidance available when difficulties/problems are encountered.

Teaching seminars (day 7, 37 and 97)

The educational intervention includes three teaching seminars on days 7, 37 and 97. All seminar days have a similar overall structure with a focus on hands-on training and the individual participant's development of scanning competences. However, the teaching aims are different on each seminar which means different focus in the teaching and different activities between seminar days.

[figure not shown]
Teaching seminar 1

The aim of the first teaching seminar is to give participants first-hand experiences with performing POCUS scans and to create a foundation of knowledge and experience which is to be further developed in the coming months. Furthermore, the participants will learn to perform five of the POCUS scans in the selected curriculum.

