After the teaching seminar a final post-self-test is available (a replication of the pre-self-test for teaching seminar 3) for the participants to create awareness about continuous learning process and to illustrate to what extent the learning objectives of the teaching seminar have been reached. The teachers will reach out to participants, where the test scores reveal problems or difficulties, as well as participants, where the demonstration of the scan revealed specific difficulties. These participants will be offered additional support.

Participant commitment

The educational intervention requires considerable commitments from the participants. This will be outlined in both the course description, the introduction webinar and on the first teaching seminar. Participants will have to allocate three whole days for the teaching seminar and considerable time to practice scanning skills especially during the training phase (days 8-29). Furthermore, time will be allocated to perform assignments and follow the discussion on the online platform.

To ensure this commitment, time will be spent on building group relations on the first teaching seminar. In addition, a teacher will be allocated each participant as a mentor during the learning process. The mentor will monitor individual progress in the online platform and correspond with the individual participant in the chat functions, provide feed-back on assignments and reach out to participants, who fail to be active on the online platform.

11b Criteria for discontinuing or modifying allocated interventions for a given trial participant

The trial may be discontinued for a GP in case of withdrawal of an informed consent. Hence, data collection will stop for that person at the time of withdrawal of the informed consent. Otherwise, this is an intention-to-treat study hence participants will not be excluded because of low adherence to the educational elements. However, we will collect data of the degree of participation for each participant.

11c Strategies to improve adherence to intervention protocols, and any procedures for monitoring adherence

The teacher will act as mentors for the participants and monitor participants' activity on the online platform. The teachers will monitor the activity of the participants, they are mentoring and reach out to participants, who fail to be active on the online platform or complete assignments.

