At baseline the following participant characteristics will be collected in a baseline questionnaire: Age (years), gender (M, F, other), seniority (year of graduation from medical school), experience (years working as a GP), previous use of ultrasound (number of years with regular use), previous ultrasound training (yes/no), scanner type (low range, mid range, high end), practice owner (yes, no), type of practice (collaboration, partnership, solo), location of practice (urban, rural, mixed), distance to the nearest imaging facility, number of patients assigned to the practice, and number of GPs working in the practice. In addition, we will register GP's participation in educational activities during the educational intervention.

Characteristics of scanned patients

From PLSP, we will receive the aggregated data (age, gender) on patients, who have had a POCUS fee-specific code registered in their medical record during the study. Age and gender are calculated based on patient ID in the medical records in the clinics (CPR numbers). These data are extracted and transferred to CAM AAU anonymously.

The collected characteristics of participating GPs and scanned patients will be used to describe the population and to do sensitivity analyses.

13 Time schedule

Approval of the study by Danish Regions and PLO: June 2022

Allocation of clusters: June 2022

Recruitment: June – September 2022

Registration of the study in Clinical Trials: October 2022

Participant allocation: October 2022

Ethical approval: November 2022

Data collection: (Time of data collection for each cluster is illustrated in Figure 2).

- Retrospective data collection using register data (Primary outcome P1 and P2 and secondary outcome S2 and S5): January 2023 – June 2024.
- Prospective data collection using GP questionnaires (Secondary outcome S2-S4): November 2022 – May 2024.
- Prospective data collection using patient questionnaires (Secondary outcome S6 and S7): June 2023 – June 2024
- Prospective data collection using GPs' registration of unwanted cases (outcome S8): January 2023 – June 2024.

- Background characteristics on participating GPs are collected at the first teaching seminar: January 2023 – January 2024.
- Retrospective evaluation of medical records are collected in July – October 2024.

Cleansing of data and data analysis: July 2024 – December 2024

Reporting of the study: 2025

14 Sample size

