5.1. The primary outcomes

Outcome P1:

The number of monthly scanning-specific remuneration codes will be summarized for each participating GP from October 2022 to June 2024. In a stepped wedge analysis model, we will compare the number of scanning-specific remuneration codes BEFORE the intervention to the number of scanning-specific remuneration codes AFTER the intervention.

In addition, we will report the overall frequency of participating GPs, who use the scanning-specific remuneration codes in the end of the study (May and June 2024).

Outcome P2:

The number of monthly referrals will be summarized for each participating GP from October 2022 to June 2024. In a stepped wedge analysis model, we will compare the number of referrals sent by participating GPs BEFORE the intervention to the number of referrals sent AFTER the intervention.

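### Seminar absence falls only around each cluster's crossover, so the SAP's assumption of comparable absence can shift P2 and S1 by about 4%, with a sign set by a coding of the course months that the SAP leaves open

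*SAP*

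**What the plan says.** SAP section 9.2 states that over the 21 months "participating GPs will be absent from the clinic due to vacation, short illness, course participation etc" and that this will cause variation in activity. It then sets the matter aside by assuming that "planned absence from the clinic is comparable". Only extraordinary absence, withdrawal and failed extraction are treated as missing data.

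Protocol section 11a (Participant commitment) gives the size of the seminar absence: "Participants will have to allocate three whole days for the teaching seminar". The same section schedules "three teaching seminars on days 7, 37 and 97". Figure 2 marks three consecutive course months per cluster and shows them as a phase of their own, between the control period and the intervention period.

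For P2, SAP section 5.1 says "we will compare the number of referrals sent by participating GPs BEFORE the intervention to the number of referrals sent AFTER the intervention". S1 in section 5.2 is handled in the same way. The model in SAP section 9 is a linear mixed model with random cluster and participant effects, fixed step effects, a national time trend and prior POCUS experience. Protocol section 7 words hypothesis P2 differently, as a fall in referrals divided by consultations.

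**The concern.** Ordinary holiday and short illness may well average out across clusters. Seminar absence does not. It falls in the course period of each cluster and nowhere in its control months, so it is tied to the crossover that defines the comparison. Step effects and the national trend cannot absorb it, because the dip falls in different calendar months for different clusters.

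The SAP requests every month from October 2022 to June 2024 and never says what a course month is. If course months count as intervention, days spent in a seminar can look like fewer referrals, which is the direction P2 predicts. If they count as BEFORE, they depress the comparator and can hide a real fall. S1 has no predicted direction, so there the result would be a spurious change in consultations.

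**Working it through.** The documents give no effect size, SD, power or bias figure, so there is nothing of the plan's own to reproduce.

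**Inputs from the documents**
- 10 clusters of 20 GPs over 21 monthly steps (Protocol section 8, Figure 2).
- First course month per cluster, read from Figure 2: 4, 5, 5, 6, 7, 8, 9, 10, 11, 12. Each cluster has three consecutive course months.
- Month fixed effects with cluster and participant random intercepts (SAP section 9).

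**Assumptions not in the documents**
- One clinic day lost per course month out of about 21, so the dip is 1/21 = 4.76%.
- Seminars fall on clinic days, and the lost work is not made up.
- Cluster/participant variance shares of 0.01/0.3, 0.05/0.5 and 0.1/0.7.

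**Step 1: weight on the course months.** Generalised least squares was applied to this layout, with course months coded as intervention. In the middle setting the treatment estimate puts weights of 0.376, 0.291 and 0.222 on the three course months, which sum to 0.889. Over the three settings the sum is 0.877 to 0.891. With AR(1) correlation of 0.3 it is about 0.94. A plain average over AFTER months would give only 30/143 = 0.21 (30 course months among 143 post-crossover cluster-months). The stepped-wedge estimate leans on the months just after crossover, so the dip is hardly diluted.

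**Step 2: shift with no true effect** (multiplier × dip)

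| Course months coded as | Multiplier | Shift, 1 day in 21 |
|---|---|---|
| Intervention | -0.889 | -0.889 × 4.76 = -4.2% |
| BEFORE | +0.889 | +4.2% |
| Excluded | 0 | 0 |

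At 22 clinic days per month the shift is about 4.0% in size (0.877/22); at 16 days it is about 5.6% (0.891/16). If half the lost work is caught up, 4.2% becomes 2.1%.

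**Step 3: seminar timing.** Days 7 and 97 are 90 days apart, so the third seminar would usually fall in a fourth calendar month, whereas Figure 2 shows three consecutive months. With the third seminar in the fourth month and course months coded as intervention, the multiplier falls to about 0.83, and 0.83 × 4.76 = 3.95, still about -4%.

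**Step 4: false significance, course months coded as intervention.** At a GP-month residual SD of 30% of the mean (assumption) the SE is about 1.96%, so z = 4.23/1.96 = 2.16 and the two-sided 5% rejection probability is Φ(2.16 - 1.96) + Φ(-2.16 - 1.96) ≈ 58%. The SE scales with the SD.

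| Residual SD (% of mean) | SE | No catch-up | Half catch-up |
|---|---|---|---|
| 30 | 1.96% | 58% | 19% |
| 50 | 3.27% | 25% | 10% |
| 80 | 5.23% | 13% | 7% |

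**Step 5: the protocol's rate.** If absence cuts referrals and consultations in the same proportion, the ratio is unchanged (0.952/0.952 = 1) and the P2 shift is about 0. This does nothing for S1.

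**The case against.** The strongest reply is that nothing here is certain to happen. A reader might infer that counts must fall and that the fall will pass for a POCUS effect on referrals. The documents do not support that. They do not say that seminars fall on a GP's clinic days or that appointments are not moved. GPs are self-employed and partly paid by fee for service (Protocol section 9), so catch-up is plausible. The shift favours hypothesis P2 only if course months count as intervention; Figure 2's separate phase would equally allow their exclusion, which gives zero. This all stands, and it limits the claim to a conditional one.

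The false-positive figures also rest on an assumed SD. Besides the range in the table, a cluster-by-month SD of 5-7% of the mean would cut the 58% to 32-41%. With no target effect in the documents, a shift of 2-4% cannot be called large or small against the trial's own aim.

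On S1 it can be argued that the course is the intervention, so consultations lost to training are a real, if passing, consequence under intention to treat. That is fair, but the planned estimate would not measure it well. Averaged over the AFTER months the dip is 0.21 × 4.76 = 1.0%, while the model would report about 4.2%.

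The protocol's referral rate would protect P2. However, SAP section 5.1 analyses the count, so that protection is not in force.

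**Conclusion.** The point holds in conditional form. SAP section 9.2 makes a comparability assumption that the trial's own timetable contradicts for seminar days, and nothing in the P2 and S1 analysis compensates. Either way of including the course months biases the estimates: about 4% in size at one uncompensated day in 21, about 2% with half catch-up. The sign depends on a coding the SAP does not give. The size rests on the assumed number of clinic days, the absence of catch-up and the layout read from Figure 2. The false-positive probability cannot be fixed without an SD. This should be corrected before analysis, but the documents do not show that it invalidates P2.

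**What to change.** In SAP section 9.2, restrict the comparability assumption to absence other than seminars. In sections 5.1, 5.2 and 9, state how course months are coded. Then remove the seminar effect from P2 and S1 in one of two ways.

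- **Covariate.** Add the number of seminar days the GP attended in that month. This estimates the dip and so needs no assumption about catch-up. The protocol already plans to register "participation in educational activities during the educational intervention" (section 12), and SAP section 10.2 describes a fixed course timeline. If every GP attends one seminar in each course month, the covariate equals a course-month indicator, and intervention and BEFORE coding then give the same treatment estimate.
- **Transition phase.** Exclude the course months. Define them by the actual seminar dates, because days 7, 37 and 97 do not fit the three months of Figure 2; those passages need reconciling. A seminar outside the excluded months would bring the shift back.

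Report the alternative codings and a per-available-day analysis as sensitivity analyses. The latter should not be primary: it assumes no catch-up and over-corrects by about 2% if half the work is made up and about 4% if all is. Individual working days are also not among the listed variables.

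Reconcile the SAP's P2 count with the protocol's referrals per consultation, and state which is primary.

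The cost is SAP wording, one derived variable and some precision. At an SD of 30% the SE rises from about 1.95% to about 2.6% with the covariate (2.6/1.95 = 1.33) or 2.9% with exclusion (2.9/1.95 = 1.49).

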The data management will follow the rules of GDPR and the Danish Data Protection Agency. All study data will be stored on a secure server at Aalborg University. Questionnaire data will be collected using the online platform SurveyXact (Rambøll, Aarhus, Denmark). A data management agreement has been made between Rambøll and Aalborg University. At the end of the data collection, data will be moved from SurveyXact to Aalborg University's server. Register data will be collected by PLSP. Data management agreements between PLSP and Aalborg University will be made prior to the collection of data. PLSP will receive data from the different IT suppliers for the general practice clinics. Data management agreements between the IT suppliers and PLSP as well as the GP clinics and the IT suppliers already exists. For this specific study, we will develop an instruction for the GPs to incorporate in the existing data management agreement prior to the collection of data.

20a Statistical methods for analysing primary and secondary outcomes.

All statistical analyses will be performed using STATA version 17 (StataCorp, Texas, USA).

The principles of Intention-to-treat is followed in the analysis. If a GP e.g. misses one teaching seminar, we will still consider the GP has having completed the educational intervention. Data will be analyzed according to a pre-established Statistical Analysis Plan (SAP) in consultation with a statistician. For the primary outcomes (continuous data), we plan to use linear regression models adjusting for the fixed effect of time and the random effects of clusters.

Due to the nature of the study the intervention cannot be blinded to the participants, but for statistical assessment, data will be blinded as regard to time of collection and location.

20b Methods for any additional analyses (e.g. subgroup and adjusted analyses).

Sensitivity analyses and sub-analyses will be performed to explore the importance of different educational elements in the intervention and background characteristics of participating GPs. These sub-analyses will be defined in the statistical analysis plan.

20c Missing data

A sensitivity analysis will be performed in cases, where missing values are not considered random.

Data monitoring

21a Data monitoring committee (DMC).

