6.2. GP questionnaires

The questionnaire will be collected through SurveyXact (Rambøll, Aarhus, Denmark).

Data from the BEFORE and AFTER questionnaire will be extracted from the online survey tool as excelfiles and merged in Stata prior to the analysis.

GPs report of adverse events will be extracted from SurveyXact as excelfiles.

7. Sample size

This is a pragmatic trial where size of the sample is given by the collective agreement between PLO and the Danish Regions. We plan to make post-hoc power calculations to discuss the needed of recruitment in future similar studies. The power calculation will not be used to discuss the results in current study (5,6).

8. Safety committee

A safety committee was set up to handle all reports of adverse and suspected adverse events (AEs) and serious adverse events (SAEs). [name] headed the committee. The safety committee had the mandate to end the trial.

9. Statistical analysis

Data will be cleaned, and quality assurance will be performed to secure validity and completeness. All statistical analyses will be performed in Stata (IC version 18).

For the data analysis of P1, P2 and S1, we will receive individual GP data for the number of monthly remuneration codes (Scanning activity), referrals (Activity outside general practice) and consultations (Activity in general practice), from October 2022 to June 2024. For this period, we will also receive practice level data.

For outcomes P1, P2 and S1, we will use a linear regression mixed model adjusting for the random effect of clusters and participants, the fixed effect for steps in the analysis as well as the time trend (Data on the background population) and the effect coming from some participants' prior experience with POCUS. The time trend will be estimated from the variation in remuneration codes and referral in all GPs clinics in Denmark in the period October 2022 to June 2024.

All above mentioned analyses will be performed as complete case analyses. We will perform sensitivity analyses to (1) explore the effects of missing data using imputation of missing and (2) the time trend in our data compared to the time trend in the background population.

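### No planned analysis lets GPs who withdraw differ systematically from those observed, and the Protocol 20c sensitivity analysis for non-random missingness is not carried into the SAP

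*SAP*

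**What the plan says.** For P1, P2 and S1, SAP section 9 states "we will use a linear regression mixed model adjusting for the random effect of clusters and participants", and then "All above mentioned analyses will be performed as complete case analyses". It does not say whether an incomplete case is a GP-month or a whole GP. Two sensitivity analyses follow: one to "explore the effects of missing data using imputation of missing", the other comparing time trends.

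SAP 9.2 says "Missing data for participants will also occur if a participant withdraws from the study". It lists this beside extraordinary absence, months that cannot be extracted, and clinics that supply no GP-level data. One two-step rule covers all of them. Step 1 uses practice-level data if no colleague takes part and the overlap is plausible. Step 2 reads "In other cases of missingness, we impute data based on available data separately for each of the ten clusters", and names the cluster and the clinic as sources. No imputation model, covariates or number of imputations is given.

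Protocol 11b ends data collection on a GP when consent is withdrawn, and adds that "participants will not be excluded because of low adherence to the educational elements". Protocol 20a adopts intention-to-treat. Protocol 20c says "A sensitivity analysis will be performed in cases, where missing values are not considered random".

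For the last two study months, May and June 2024, SAP 5.1 says "we will report the overall frequency of participating GPs, who use the scanning-specific remuneration codes in the end of the study". No denominator is stated.

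Neither document gives an expected withdrawal rate or any information on how much withdrawing GPs scan.

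**The concern.** P1 is the trial's measure of uptake (Protocol 8), so GPs who turn away from POCUS are part of the answer. Once a GP withdraws consent, the later months are unobserved. The main analysis leaves them out and the sensitivity analysis fills them from observed data. Both rest on the same premise: unobserved months resemble observed ones. If withdrawal goes with low use, the two analyses can agree closely and both be wrong, and a reader would take the agreement as reassurance.

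A link between withdrawal and low use is plausible but not documented. Protocol 11a describes a heavy time commitment, and Protocol 6 reports GPs' concerns about workload. Under Protocol 9 the POCUS fee becomes claimable only after course attendance, so a GP who leaves before the course may well register few or no codes.

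**Working it through.** **1. Is the 20c analysis anywhere in the SAP?** The SAP has two sensitivity analyses for these outcomes. Imputation draws only on observed practice, cluster or clinic data. The other concerns the time trend. Neither allows unobserved values to depart systematically from observed ones, and the SAP does not mention non-random missingness.

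**2. Size when GPs leave before any post-course month.** The plan gives no figure to reproduce, so the inputs below are assumptions.

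- w = share of GPs withdrawn
- r = withdrawers' post-course use relative to stayers'
- m = stayers' post-course mean

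Mean over all GPs = (1 − w)m + w·r·m = m[1 − w(1 − r)]. The observed mean is m. Factor = 1/[1 − w(1 − r)].

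| w (of 200 GPs) | r = 0 | r = 0.5 | r = 1 | r = 1.5 |
|---|---|---|---|---|
| 5% (10) | 1/0.95 = 1.053 | 1/0.975 = 1.026 | 1.000 | 1/1.025 = 0.976 |
| 10% (20) | 1/0.90 = 1.111 | 1/0.95 = 1.053 | 1.000 | 1/1.05 = 0.952 |
| 20% (40) | 1/0.80 = 1.250 | 1/0.90 = 1.111 | 1.000 | 1/1.10 = 0.909 |

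**3. Does the mixed model change this?** A small simulation used the Figure 2 layout: 10 clusters of 20 GPs, months 3–21, course months left out, fixed months, random cluster and GP effects. Assumed values were a stayer effect of 10 codes a month and SDs of 1 (cluster), 2 (GP) and 3 (residual). Imputation was from the cluster only. There were only 6 replicates per scenario, so results are good to roughly 0.1–0.3.

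| Scenario | True effect | GP-month complete case | Whole GP excluded | Cluster imputation |
|---|---|---|---|---|
| Before any post-course month, w = 10%, r = 0 | 9.0 | 10.1 | 10.1 | 10.1 |
| Before any post-course month, w = 20%, r = 0 | 8.0 | 9.9 | 9.9 | 10.0 |
| Before any post-course month, w = 20%, r = 1 | 10.0 | 9.8 | 9.8 | 9.8 |
| Before any post-course month, w = 20%, r = 1.5 | 11.0 | 9.9 | 9.9 | 9.7 |
| Three months after course, w = 20%, r = 0 | 8.0 | 7.9 | 10.1 | 7.6 |

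In the second row all three approaches overstate by about 24% (9.9/8.0 = 1.24), and imputation does not reveal it. In the third row the shortfall is simulation noise: the same fit on complete data gave 9.7. In the last row the model has three observed months of low use per withdrawer and recovers the truth if GP-months are kept. Excluding whole GPs does not recover it. That scenario assumes constant use after the course. A decline in use that leads to withdrawal was not simulated.

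**4. The May–June 2024 proportion.** A plain proportion has no GP effect to protect it. If 120 GPs use the codes (assumed) and no withdrawn GP does, uptake over all enrolled is 120/200 = 60%. With 20 withdrawn GPs left out it is 120/180 = 66.7%; with 40 left out, 120/160 = 75%.

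**The case against.** A reader might infer that withdrawn GPs are dropped from P1 altogether, that their months are filled only from GPs who kept scanning, and that both analyses therefore overstate uptake. The documents do not support that reading.

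- Only months after withdrawal of consent are clearly lost, and a mixed model with a participant effect can keep the earlier ones. This stands, but the SAP does not say that it will keep them.
- GPs who stop scanning without withdrawing consent stay in and contribute low or zero counts. So it does not follow that uptake looks better the more GPs give up. This stands.
- Imputation step 1 uses the GP's own practice, whose codes may largely reflect that GP's scanning. This stands in part. The overlap is closest in a solo practice, but there the practice data are essentially the withdrawn GP's own, and Protocol 11b ends collection on that person. Elsewhere step 2 applies.
- The direction of bias is an assumption. This stands, and it is the reason to vary it in a sensitivity analysis.
- Protocol 20c is conditional and names no method, and the SAP does not revoke it. True. But Protocol 20a relies on a pre-established SAP, and without a method there the choice is made after the data are seen.
- The uptake denominator is unstated, which is not the same as a planned exclusion. This stands.
- SAP 9.1 will report reasons for dropout. That helps a reader judge, but quantifies nothing.

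**Conclusion.** The gap is real and conditional. Neither the complete-case analysis nor the planned imputation allows for withdrawal related to use, and the SAP does not carry out Protocol 20c. If withdrawers scan less than stayers, P1 may be overstated in both analyses, by a factor of up to 1/[1 − w(1 − r)] when they leave before any post-course month. That is 1.05, 1.11 and 1.25 at r = 0 for assumed withdrawal of 5%, 10% and 20%. There is no bias at r = 1, and it reverses above 1. It is small for a GP-month model when several post-course months have been observed and use is steady. The May–June 2024 proportion would be inflated for any r below 1 if withdrawn GPs are left out. An actual overstatement cannot be claimed, because neither w nor r is given. This is a worthwhile, inexpensive repair and does not invalidate the design.

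**What to change.** 1. In SAP 9, state that complete case refers to GP-months, so that every observed month of a withdrawn GP is kept.
2. In SAP 9.2, separate withdrawal from technical missingness and keep the current imputation for the latter.
3. For withdrawals, add a delta-type sensitivity analysis that fulfils Protocol 20c. Let P1 codes in months that are both post-withdrawal and post-course (by the cluster's schedule) range from 0 to 100% of the stayers' level in the same cluster and month. Zero is the conservative bound. Do not set control months to zero, since that could lower the control mean. For P2 and S1, specify a corresponding range that follows calendar month, not a fixed pre-course mean.
4. In SAP 5.1, report May–June 2024 uptake over all enrolled GPs, counting withdrawn GPs as non-users, beside the observed-only figure.

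The cost is a few sentences and some additional model runs. The lower bound will look less favourable, and should be labelled as a bound.
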